### 3.5.8 Analytic plan

All analyses will be according to the principle of intent-to-treat, i.e., analysis of site and individuals within the site as randomized. The primary individual-level outcomes are achieving three elements of the HCV treatment cascade (diagnosed, treated, achieving SVR). We have powered the study based on a comparison of the proportions among the three groups (see below). The denominator for all cascade indicators is the number of OAT patients who are screened positive for HCV and are enrolled in the study. The numerators, the number who completed the pre-treatment evaluation, started DAA treatment and achieved SVR, will be obtained from the electronic clinical data collection system. Data will be assessed for missingness. A repeated measures likelihood based mixed model with missing at random (MAR) assumptions will be used for the analysis of the primary outcome to compare the three allocations, adjusted for the stratification variables (geographic region) plus age and gender. We will also adjust for covariates that are predictive of missingness to be consistent with the MAR assumption. Sensitivity analyses as described below will be done to assess this assumption, which is a reasonable starting point given missing data is expected to be low. Results will be displayed as point estimates with corresponding 95% confidence limits. The primary (and secondary) outcomes will be tested at the 5% (2-sided) significance level.

Hypotheses

1) OAT facilities implementing the simplified integrated model will have adoption and penetration of HCV care elements, that will ultimately result in improved patient-level outcomes like HCV cure compared to standard of care (SOC);

2) Compared to No ECHO, clinicians at ECHO-facilitated sites will have improved HCV care cascade outcomes.

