In addition, we have planned to test for a linear trend among the intervention levels for the proposed outcomes, testing that SHIM+ECHO > SHIM with No ECHO > SOC. We also plan to test the treatment effects using similar methods for OAT dropout strata separately. In addition to direct effects, mediation and moderation regression will be conducted as described by Donaldson. Testing will be conducted at a Bonferroni corrected type I error level of 0.025 to control for multiple testing. Secondary and process outcomes will similarly be tested. These measures and their subscales will be compared as pre/post and over time using one-way ANOVA/Duncan test, with general linear models to identify differences in treatment effect stratified by the geographic region (cluster). Mean scores will be normalized, with comparisons between the three groups, with the referent being SOC. To address multiple testing, we will use the Benjamini-Hochberg method of controlling the false discovery rate. We do not expect missing data to be a concern since most of the data on primary outcomes will be derived from clinical source documentation; for the survey data, we expect that we will collect more than 90% of the data at the 24-week time point. We will, however, explore all patterns of missing data and compare those with and without data to determine whether the data may be MAR or not MAR (i.e. eliminate the missing completely at random assumption). We will conduct sensitivity analyses using an appropriate missing data method, such as multiple imputation.

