### 3.5.9 Power Analysis

We will need a sample size of 133 per group (total sample size of 399), to have 90% power at a 5% level of significance to detect a standardized effect size of 0.20 for a null hypothesis of no difference between the proportions in the three groups versus an alternative of at least one difference at the 24-week time point. Additionally, we will have 94% power with a 2.5% type I error rate (Bonferroni corrected) to detect a standardized effect size of 0.32 within each geographic strata. Conservatively, we expect a 10% loss of information at the 24-week time point. Therefore, we have inflated the sample size by 10% and will recruit a total of 480 patients for the Aim 3 outcomes.

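### The checks named for the MAR assumption cannot test it: comparing patients with and without data can only contradict MCAR, and standard multiple imputation shares the MAR assumption of the main model

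*Combined protocol and SAP*

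**What the plan says.** Section 3.5.8 (Analytic plan) states the main assumption: "A repeated measures likelihood based mixed model with missing at random (MAR) assumptions will be used for the analysis of the primary outcome". It supports that assumption by adjustment: "We will also adjust for covariates that are predictive of missingness to be consistent with the MAR assumption". It then makes a promise: "Sensitivity analyses as described below will be done to assess this assumption".

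What follows later in the same section consists of two steps. The first is an exploration of missingness in which the team will "compare those with and without data to determine whether the data may be MAR or not MAR". A bracket directly after these words glosses the purpose as removing MCAR. The second is: "We will conduct sensitivity analyses using an appropriate missing data method, such as multiple imputation". No delta adjustment, tipping-point analysis, reference-based imputation, pattern-mixture model or selection model is named anywhere in the document.

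On the amount of missing data, 3.5.8 states: "for the survey data, we expect that we will collect more than 90% of the data at the 24-week time point". Section 3.5.9 (Power Analysis) states: "Conservatively, we expect a 10% loss of information at the 24-week time point".

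Among the named endpoints, the one this touches is essentially S3a, quality of life. Section 3.5.5 measures S2a (motivation) at baseline only, and 3.5.6 collects S2b and S2c on a form completed by clinic staff rather than in the survey.

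**The concern.** The plan asks whether data are MAR or not MAR. Its first step compares the observed characteristics of patients with and without data, and the null hypothesis of that comparison is MCAR. If missingness depends on observed variables, the comparison should reject even though MAR holds and the adjusted analysis is sound. If missingness depends on the unseen follow-up value, the comparison reacts only so far as that value is linked to something observed. A rejection therefore does not count against MAR, and a non-rejection does not count in its favour.

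The second step does not close the gap. Standard multiple imputation fills in missing values from the distribution of observed values given covariates. That is the assumption the likelihood-based mixed model already makes, so agreement between the two is not evidence for it.

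What is at stake is the arm comparison of quality of life at follow-up. Arm-dependent non-response is possible because SOC patients are referred elsewhere for HCV care (3.1.1), while most SHIM patients are treated where they receive OAT (3.1.2). Both checks could look reassuring while the comparison is off. In addition, section 3.6 deletes the data of participants who choose to withdraw, so those patients cannot enter the with/without-data comparison at all.

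**Working it through.** The point concerns method, and the plan gives no figure to reproduce. The illustration below shows whether the two named checks can miss a bias, and how large that bias could be.

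**Inputs from the document.** 160 patients per arm (section 3.5). 10% missing (3.5.9, consistent with more than 90% complete in 3.5.8). 17% as an upper end, from the retention above 83% at 12 months that 3.5.7 reports for earlier studies.

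**Assumptions.** Two arms, individual-level data, no clustering and no true effect. Baseline-outcome correlation ρ = 0.5, so y = 0.5·b + √0.75·u, where b is the baseline score and u is independent of it. In one arm (SOC in this example), the log-odds of missingness rise by 1.5 per SD as u gets worse. In the other arm, missingness is random at the same rate. A 5% missing rate is added as a low end.

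**Simulation, 1,500 runs per row.** The check is a t-test of baseline between patients with and without data. The MAR analysis is baseline-adjusted regression on observed cases, which is equivalent to a MAR likelihood analysis with one follow-up. Multiple imputation (MI) uses 20 imputations with arm and baseline in the model.

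| Missing | Check rejects | Bias, MAR analysis | Bias, MI |
|---|---|---|---|
| 5% | 5.5% | −0.058 SD | −0.059 SD |
| 10% | 5.5% | −0.103 SD | −0.103 SD |
| 17% | 5.3% | −0.168 SD | −0.169 SD |

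The MI and MAR estimates correlated at 0.996 to 0.999 across runs. The sign follows from placing the mechanism in SOC: losing its worse patients makes SOC look better. Placing it in a SHIM arm reverses the sign.

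**Exact check of the 10% row.** With missing fraction r = 0.10 and slope 1.5, numerical integration gives a mean u of −1.095 among the missing. Then:

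- Mean u among the observed = 0.10 × 1.095 / 0.90 = 0.122.
- Bias = −√0.75 × 0.122 = −0.866 × 0.122 = −0.105 SD, against −0.103 simulated.

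The same calculation at slopes 1 and 2 gives −0.079 and −0.124 SD at 10% missing, and −0.129 and −0.197 SD at 17%.

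**Two contrasts.**

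- Same outcome-dependent mechanism in both arms: the arm difference was unbiased, within 0.002 SD.
- True MAR, with missingness in one arm depending only on observed baseline, 10% missing: the check rejected in 83% of runs, although the adjusted estimate was unbiased (−0.002 SD).

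**What a delta adjustment would show.** If missing values in one arm are δ SD away from what MAR predicts, the arm difference moves by r × δ. At 10% missing, δ = 0.25, 0.5 and 1.0 move it by 0.025, 0.05 and 0.10 SD. The mechanism in the 10% row corresponds to δ = 0.866 × (−1.095 − 0.122) = −1.05 SD, and 0.10 × 1.05 = 0.105 SD, which matches the bias. A range of shifts that stopped at −0.5 SD would cover only about half of it.

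**The case against.** The strongest reply is that the sentence should be read whole. With its bracket and the hedged verb, it can mean that MCAR will be ruled out, leaving data that may be MAR or not. The comparison can serve that purpose. It is a fair reading and may be what the authors meant. It still leaves nothing in the section that assesses MAR, which is what the section promises.

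Second, the plan does not call its imputation MAR-based. The words introducing multiple imputation leave room for an MNAR version, and delta-adjusted imputation is itself multiple imputation. This stands: nothing is excluded. But no MNAR version is specified, and the standard form assumes MAR.

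Third, the illustration makes missingness depend on a part of the outcome that is independent of baseline, so the check's 5% rejection rate is built in rather than discovered. This also stands. If missingness tracked observed baseline as well, the comparison might react, but that would contradict only MCAR. Tabulating missingness by arm, a natural part of exploring all patterns, could reveal unequal rates. The table above keeps the rates equal, so it would show nothing in that case. The illustration also leaves out the intermediate survey, the covariates predictive of missingness, and clustering with four clinics per arm.

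Fourth, a mechanism that differs by arm is not established. An independent interviewer surveys all arms on one schedule (3.5.6), and retention contact runs through OAT clinics in every arm (3.5.7). This weakens the likelihood of bias but does not remove the possibility.

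A reader might infer that the survey results are biased, that any bias would necessarily pass the checks, or that the cascade endpoints are compromised. The documents support none of these. Bias in the arm difference needs an arm-specific mechanism. The checks can miss it but need not. Section 3.5.8 expects most primary-outcome data to come from clinical source documents.

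**Conclusion.** The concern holds as a gap between a promise and the methods named to keep it. The comparison can contradict MCAR but cannot decide MAR versus not MAR, and multiple imputation in its standard form repeats the main model's assumption. Neither conclusion depends on the simulation.

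The practical consequence is moderate and confined essentially to S3a, a secondary endpoint. If non-response depends on unseen outcomes in one arm only, the bias is about 0.1 SD at 10% missing (0.08 to 0.12 SD for slopes of 1 to 2). At 17% it is 0.13 to 0.20 SD, but that rate comes from other studies at 12 months and exceeds what this plan expects. If the mechanism is the same in all arms, the bias is near zero. The correlation, slopes and mechanism are assumptions, and clustering is ignored, so these sizes are illustrative. No false-positive rate should be read from them. The change is worth making, but the trial's primary conclusions do not depend on it.

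**What to change.** In section 3.5.8, state that the comparison of patients with and without data, including missingness by arm, is used to rule out MCAR and to choose auxiliary covariates for the MAR model. State also that it is not used to decide between MAR and not MAR.

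Name a delta-adjusted (pattern-mixture) multiple imputation of the follow-up survey outcomes as the sensitivity analysis for MAR. Vary the shifts separately by arm, do not cap them at −0.5 SD, and extend them until the conclusion changes. Report that tipping point so readers can judge whether a departure of that size is plausible. MAR-based imputation may stay as a supplementary analysis, but not as the test of MAR.

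The cost is a few sentences in the plan and some extra runs on data already due to be collected. The downside is that some survey conclusions may have to be reported as sensitive to missing data.

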### 3.5.9 Power Analysis

We will need a sample size of 133 per group (total sample size of 399), to have 90% power at a 5% level of significance to detect a standardized effect size of 0.20 for a null hypothesis of no difference between the proportions in the three groups versus an alternative of at least one difference at the 24-week time point. Additionally, we will have 94% power with a 2.5% type I error rate (Bonferroni corrected) to detect a standardized effect size of 0.32 within each geographic strata. Conservatively, we expect a 10% loss of information at the 24-week time point. Therefore, we have inflated the sample size by 10% and will recruit a total of 480 patients for the Aim 3 outcomes.

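### The sample-size inputs in 3.5.9 do not give 133 per group: the three-group test described needs 317 in total at 5%, and the within-region power does not reproduce either

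*Combined protocol and SAP*

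**What the plan says.** Section 3.5.9 (Power Analysis) gives the basis of the trial size: "We will need a sample size of 133 per group (total sample size of 399), to have 90% power at a 5% level of significance". The effect is set in the words "to detect a standardized effect size of 0.20", and the hypothesis is "no difference between the proportions in the three groups versus an alternative of at least one difference at the 24-week time point". The same paragraph adds "94% power with a 2.5% type I error rate (Bonferroni corrected) to detect a standardized effect size of 0.32 within each geographic strata". It does not name the effect-size metric, the test statistic, the degrees of freedom or the software.

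Section 3.5.8 (Analytic plan) gives two test levels. For the outcomes in general: "The primary (and secondary) outcomes will be tested at the 5% (2-sided) significance level". Later, after the trend test, the analyses by OAT dropout stratum and the mediation and moderation analyses: "Testing will be conducted at a Bonferroni corrected type I error level of 0.025 to control for multiple testing". Section 3.5.4 lists three primary endpoints, P1 to P3. No section mentions 0.0167 or a split of alpha over three tests.

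**The concern.** A reader who enters the five stated inputs (three groups, proportions, effect 0.20, 90% power, 5%) into a standard power routine gets a clearly smaller number than 399. At least one input is therefore not the one used. This paragraph is the only justification of the Aim 3 sample size, so the reader cannot tell which test, effect or significance level the trial was sized for.

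Two things are at stake. The first is the effect the trial can detect: w = 0.20 over three groups and d = 0.40 between two groups are different targets. The second is the success threshold. Section 3.5.8 gives 5% and then 2.5%, and the sizing paragraph, which could have settled the matter, does not reproduce at either level for the test it describes.

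**Working it through.** **Inputs.** From 3.5.9: three groups, effect 0.20, 90% power, alpha 0.05, 399 in total; within region, effect 0.32, alpha 0.025, claimed power 94%. From 3.5.1: three clinics per region at 40 patients each, so 3 × 40 = 120 per region (480/4). Assumption: the effect is Cohen's w, the usual standardized effect for a chi-square test of proportions. Patients are treated as independent throughout.

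**Step 1: the plan's figure for the test it describes.** Power = P(noncentral chi-square with 2 df and noncentrality λ exceeds the central critical value), where λ = N·w² = 0.04·N. Solving for 90% power:

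| Alpha | Critical value | λ for 90% | N = λ/0.04 | Total (per group) | Power at 399 |
|---|---|---|---|---|---|
| 0.05 | 5.991 | 12.654 | 316.3 | 317 (106) | 95.6% |
| 0.025 | 7.378 | 14.753 | 368.8 | 369 (123) | 92.4% |
| 0.05/3 | 8.189 | 15.949 | 398.7 | 399 (133) | 90.0% |

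The stated 5% does not give 399, and neither does 2.5%. Solving for alpha at N = 399 and 90% power gives 0.0166.

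**Step 2: another metric for the same three-group test.** A one-way ANOVA with f = 0.20 needs about 320, 373 and 403 in total at the same three alphas. The mismatch at 5% does not depend on choosing w over f.

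**Step 3: two-group calculations at the stated 5%.**
- For two groups, f = 0.20 corresponds to d = 2 × 0.20 = 0.40. The normal approximation gives n = 2(1.960 + 1.282)²/0.40² = 131.3. The t test gives 132.3, so 133 per group, an exact match.
- A 1-df chi-square with w = 0.20 gives N = 10.507/0.04 = 262.7, so 131.3, or 132 per group.

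**Step 4: the within-region claim.** λ = 120 × 0.32² = 12.288.

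| Test | Alpha | Power |
|---|---|---|
| 2 df | 0.025 (as stated) | 83.0% |
| 2 df | 0.05 | 89.1% |
| 1 df | 0.025 | 89.7% |
| 1 df | 0.05 | 93.9% |

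The stated 94% appears only in the last row. For 2 df at 2.5%, even 160 patients in a region would give 93.1%.

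**Step 5: the two sentences together.** The three-group test at 0.05/3 explains the first figure exactly but not the second. A two-group (1-df) calculation at 5% gives 132 to 133 per group for the first and 93.9% for the second. It fits both numbers, but it contradicts the described three-group test in the first sentence and the stated 2.5% in the second.

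**The case against.** The strongest defence is that the stated 5% may be correct. Section 3.5.9 names no metric or test, so reading 0.20 as w with 2 df is the reviewer's choice. A pairwise calculation with d = 0.40 at 5% returns 133 per group, and 3.5.8 also tests the outcomes at 5%. On that view the alpha is right and only the description of the test is wrong. This stands as a possible explanation. It does not remove the discrepancy, because the paragraph explicitly describes three proportions and an alternative of at least one difference.

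The defence can also say that the mismatch does no harm: for the described test, 399 exceeds both 317 and 369, so no nominal power is lost. That is correct for the three-group test before clustering. It is less comfortable if the sizing was pairwise. At 2.5%, d = 0.40 needs 156.4, so 157 per group, against 160 × 0.9 = 144 evaluable per arm after the plan's 10% loss. Whether 2.5% is meant to govern the primary comparison is itself unclear from where it stands in 3.5.8.

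In the other direction, a reader might infer that the sizing alpha was really 0.05/3, one share for each of P1 to P3, and that the plan should say so. The match in step 1 is exact and there are three primary endpoints. The documents still do not support the inference: no section mentions such a split, a two-group calculation at 5% gives the same 133, and the within-region figure does not fit it (2 df at 0.0167 with 120 per region gives 78.9%).

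**Conclusion.** The size, power, alpha and test stated in 3.5.9 cannot all be right. For the three-group test described, 5% and 90% power need 317 patients and not 399, a gap of 82. Equivalently, 399 gives 95.6% power and not 90%. The within-region power is 83.0% and not 94% at the stated 2.5%. These results assume that 0.20 and 0.32 are values of w, that each region has 120 patients and that patients are independent. The first result hardly changes with f in place of w.

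The inconsistency is certain on that reading, but its cause is not. The error may lie in the alpha, in the test described or in the effect metric. The documents support neither the conclusion that 0.0167 was the sizing alpha nor the conclusion that this discrepancy by itself leaves the trial short of power. Nor is the apparent surplus at 5% spare power, since no allowance for clinics enters any of these figures.

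**What to change.** In 3.5.9, name the test, its degrees of freedom, the effect-size metric and the alpha actually used, and restate the figures for the planned test.

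- If it is the three-group test at 5%, give N = 317 for 90% power, or 95.6% power at 399. Correct the within-region power to 83.0% at 2.5%. Mark all of these as before clustering.
- If the sizing was pairwise, or used a split alpha, replace the description of the test, effect metric and alpha with the one used. Apply that same level to P1 to P3 in 3.5.8.

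In either case, say in 3.5.8 which analyses the 0.025 level covers. Do not insert 0.0167 unless the sponsor confirms from its sizing records that it was used: doing so on inference could write a false basis into the protocol and tighten the success threshold without reason.

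The cost is a wording amendment to two sections and a look at the original calculation. It needs no new patients or data.

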#### 3.4.5 Power Analysis

The qualitative sub-study sample during the pilot phase will be limited to one focus group with patients and three in-depth interviews with providers.

In the main phase, we will conduct two focus groups with 6-8 patients, one in-depth interview with participant who have dropped out of treatment, or not completed SVR12 testing, or didn't start treatment, two in-depth interviews with 2-4 providers.

In order to conduct the proposed analysis, a sample size of 900 patients, provides more than sufficient power to conduct the proposed analyses. The use of principal component analysis (PCA), for parsimoniously grouping variables is a reductionist strategy to explain groupings of variables with multiple collinearity. The time-dependent analysis allows for detection of even small changes in the primary and secondary outcome, even if the primary (or secondary) outcome increases any of the study groups. Thus, as few as 200-300 participants in each group is more than sufficient to achieve sufficient power (>0.95) to detect an intervention effect, including a synergistic effect of intervention^[No ECHO] x intervention^[ECHO] and even by site type (by varying degrees of integration), over time.

### 3.5 Research methods for Aim 3

Aim 3: To evaluate the effectiveness of SHIM in improving the HCV treatment cascade outcomes using a cluster-randomized three-arm trial design in 480 HCV-infected patients at 12 OAT clinics

randomized to standard of care (N=160) versus SHIM with (N=160) or without (N=160) ECHO facilitation.

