### 3.5.1 Design overview

Individual randomization of subjects within each site would likely lead to a high degree of cross-contamination between the study groups because the selected interventions are designed to sustainably change the provider knowledge and practice. Therefore, we have chosen a cluster-randomized trial design, where participating sites will be randomly assigned to one of the three implementation arms. Based on our preliminary studies suggesting region-specific differences in HCV level among OAT patients, we will stratify 12 OAT sites by 4 defined geographic regions (Center, East, South, West) at a 1:1:1:1 ratio. To achieve the desired sample size (see Sample Size section) and retain equal size in each group, we will select and match 3 clinics across the 4 regions. One clinic per triplet will be randomized to one of the three arms: Standard of Care, SHIM and SHIM+ECHO (see Study Conditions), resulting in total 4 clinics per arm. Each clinic will aim to recruit 40 patients. In case of clinic's capacity the availability of DAA medication in region, the clinic's capacity to include in treatment and monitor the course of treatment of a larger number of patients) the number of participants can be increased up to 60). All sites will follow the same patient recruitment and data collection procedures.

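### The Aim 3 power calculation leaves out clustering by clinic, so the stated 90% is unsupported, and the 94% regional and >0.95 Aim 2 figures rest on patient numbers that do not match the plan

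*Combined protocol and SAP*

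**What the plan says.** Section 3.5.1 describes a cluster-randomised trial. Three clinics are chosen in each of four regions and one is assigned to each arm, "resulting in total 4 clinics per arm". Each clinic aims for 40 patients, with an allowance of up to 60 where capacity and drug supply permit. The planned total is 480, or 160 per arm.

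Section 3.5.9 gives the Aim 3 power statement:
- "a sample size of 133 per group (total sample size of 399), to have 90% power at a 5% level of significance", in order "to detect a standardized effect size of 0.20 for a null hypothesis of no difference between the proportions in the three groups".
- "94% power with a 2.5% type I error rate (Bonferroni corrected) to detect a standardized effect size of 0.32 within each geographic strata".
- A 10% loss of information is expected, and so "we have inflated the sample size by 10% and will recruit a total of 480 patients".

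Section 3.5.8 adds: "The primary (and secondary) outcomes will be tested at the 5% (2-sided) significance level". It plans mixed models but names no clinic effect for Aim 3.

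Section 3.4.5, on Aim 2, says that "a sample size of 900 patients, provides more than sufficient power to conduct the proposed analyses" and that "as few as 200-300 participants in each group is more than sufficient to achieve sufficient power (>0.95" in parentheses). It gives no effect size. The Aim 2 model in section 3.4.4 does include a site random effect.

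**The concern.** The trial uses clusters because the interventions act on providers, so outcomes within a clinic are expected to be alike. A power figure with no allowance for this holds only if the clinic effect is close to nil, and the plan gives no reason to expect that. The other figures also do not fit the design: a region holds 120 patients, and Aim 2 quotes more patients than the trial can enrol.

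Both main hypotheses rest on four clinics per arm. If SHIM or ECHO shows no clear effect, readers will take the result as coming from a trial with 90% power and lean towards concluding no effect, when the chance of missing the planned effect may be large. The regional sentence invites arm comparisons that the design cannot support.

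**Working it through.** **Inputs.** From 3.5.1: 12 clinics, 4 per arm, one per arm per region, 40 per clinic (at most 60). From 3.5.9: 399 patients, effect 0.20, alpha 0.05, power 90%; effect 0.32, alpha 0.025, power 94% within region; 10% loss; 480 recruited. From 3.4.5: 900 patients, 200-300 per group. Assumed, because not given: the standardised effect is Cohen's w for a three-group comparison of proportions (2 df), and the ICC lies between 0.01 and 0.10.

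**1. The plan's own figure.** Non-central chi-square with 2 df and λ = N·w².
- N = 399, w = 0.20: λ = 399 × 0.04 = 15.96, and power at alpha 0.05 is 95.6%, not 90%.
- 90% power at alpha 0.05 needs N of about 317 (106 per group).
- Two unstated variants reproduce 133 per group: the same test at alpha 0.05/3 (90.0%), and a two-group t-test with d = 0.40 (90.1%). The text does not show which was used, if either. Neither includes clustering.

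**2. Inflation.** 399 × 1.1 = 439 and 399 / 0.9 = 444 (rounded up). 480 / 399 = 1.203, an increase of 20%. After 10% loss, 480 × 0.9 = 432. Measured against 399, that surplus would cover an ICC of only (432/399 − 1)/35 = 0.002.

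**3. Adding clustering.** With 432 analysable patients, m = 36 per clinic. DE = 1 + 35·ICC, effective N = 432/DE, λ = 0.04 × effective N, alpha 0.05.

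| ICC (assumed) | DE | Effective N | Power, large-sample | Power, F(2,9) | Power, F(2,6) |
|---|---|---|---|---|---|
| 0 | 1.00 | 432 | 97% | 89% | 82% |
| 0.01 | 1.35 | 320 | 90% | 77% | 69% |
| 0.02 | 1.70 | 254 | 82% | 67% | 59% |
| 0.05 | 2.75 | 157 | 61% | 46% | 40% |
| 0.10 | 4.50 | 96 | 40% | 30% | 26% |

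F(2,9) uses the error df of 12 clinics in three arms; F(2,6) also spends 3 df on region.

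The largest ICC at which the large-sample test keeps 90% is (N/316.3 − 1)/(m − 1):
- 432 patients: (432/316.3 − 1)/35 = 0.010.
- 480 patients, no loss: (480/316.3 − 1)/39 = 0.013.
- 720 patients (60 in every clinic), no loss: (720/316.3 − 1)/59 = 0.022.

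**4. Within region.** 3 × 40 = 120 patients. λ = 120 × 0.32² = 12.29; power at alpha 0.025 with 2 df is 83.0%. With 108 after loss it is 78.2%. 94% needs about 166. These values ignore clustering. Each region has one clinic per arm, so the arm difference and the clinic difference are the same contrast, and no between-clinic error term can be estimated there.

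**5. Aim 2.** 900 exceeds both the planned 480 and the maximum of 12 × 60 = 720. The planned 160 per arm is below 200-300. Without an effect size, the >0.95 cannot be reproduced.

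**The case against.** A reader might infer that the design delivers none of the stated power figures. The documents do not support that for the overall 90%. They give no ICC, and the individual-level calculation has slack: 97% with 432 patients and no clustering. At ICC 0.01 the large-sample test still gives 90% with 432 patients and 92% with 480. Nor does the primary calculation use patients the trial lacks: 133 per group is below the planned 160, and below the 144 left after 10% loss.

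The allowance of 60 per clinic also counts in the plan's favour. It would give 180 per region, hence 95.8% before loss and clustering (93.4% with 162), and 240 per arm, which falls inside 200-300. That part stands, but 60 is conditional and 40 is the plan. It does not bring 900 within reach, and it does not separate arm from clinic within a region.

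The cluster-level columns depend on an analysis choice. Section 3.5.8 plans individual-level mixed models, and adjusting for region should remove some between-clinic variance. F(2,6) charges the 3 df for region but gives no credit for that variance, so it tends to understate power. For this reason the conclusion leads with the large-sample figures.

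The mismatches of 399 against 317 and of 20% against 10% run in the safe direction and cause no shortfall. The use of alpha 0.05/3 is only one possible source of 399. Aim 2 is exploratory and its model has a site effect, so its mismatch is a consistency correction and adds no weight to the Aim 3 point.

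**Conclusion.** The point holds in this form. The stated 90% power is unsupported because clustering is left out of a 12-clinic trial. With 432 patients and w = 0.20, it holds only up to an ICC of about 0.010 under a large-sample test. At an assumed ICC of 0.05, power is about 61%, or 46% with F(2,9). The size of the shortfall rests on the assumed ICC and on reading the effect size as w; the omission itself does not.

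The within-region 94% is wrong for the planned 120 patients (83.0% at best), and at any clinic size a within-region arm test lacks a between-clinic error term. The Aim 2 total of 900 contradicts the plan and cannot be reached. The alpha and inflation mismatches are lesser reporting errors. The plan should be corrected before its power figures are relied on.

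**What to change.** In 3.5.9:
- Restate power for 12 clinics of 40 with 10% loss. Give the design effect, and power or the detectable difference, over a stated ICC range, using cluster-level df that match the planned analysis.
- State the test, the effect measure and the alpha behind 133 per group, and give the true inflation (399 to 480 is 20%).
- Delete the within-region power sentence and label regional arm comparisons descriptive.

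In 3.4.5:
- Replace 900 and 200-300 with 480 and 160, remove the >0.95 claim, and note that site-level factors have n = 12.

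These are wording changes only. No extra patients, clinics or procedures are proposed. The cost is that the stated power becomes less favourable.
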